14.5 Safety Analyses

14.5.1 Adverse Events

All AEs will be coded using the most up-to-date version of MedDRA. For an individual patient, AEs that began prior to the first dose of IMP or more than one day after the final dose of IMP will not be included in the analysis.

The incidence of AEs (number and percent of patients reporting each type of AE at least once during the study) will be summarised for all AEs, by investigator attribution of relationship to IMP and by severity. The incidence of AEs will be compared among (between) treatment groups using Fisher's Exact Test for all AEs, for those AEs classified by the Investigator as possibly or probably related to IMP and for severe AEs.

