9.6 Patient Commitment to the Study

9.6.1 Duration of Patient Participation

Up to 7 days will be allowed to screen a patient at Visit 1 following informed consent. The pre-study procedures will consist of a medical history and physical examination, endoscopy, 12-lead ECG, haematology and biochemistry and urine pregnancy test for female patients of child-bearing potential.

Visit 2 (Day 0) will take place immediately after all screening results are available and within 7 days after Visit 1. Patients will be required to complete a baseline RDQ which will ask the patient to rate their symptoms over the previous 7 days and have any adverse events and concomitant medications recorded. Patients meeting the entry criteria will be randomised and then issued with either Compound Sodium Alginate Double Action Chewable Tablets or matching placebo tablets to take for 7 days.

At Visit 3, End of treatment period (Day 8, between Day 7 and day 10), unused investigational medicinal product (IMP) will be collected. Patients will be required to complete the RDQ questionnaire and OTE (overall treatment evaluation) as a measure of the responsiveness to the study therapy and undergo assessment by the Investigator for

compliance and safety (AEs, haematology and clinical biochemistry and urine pregnancy test for female patients).

Further details on the timing of study visits are provided in Section 11.2.

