11.2 Study Visits/Assessments

A patient is enrolled into a study when he or she (or a legal representative as defined in Section 16.2) has signed the informed consent form, i.e. prior to any study-specific assessments being performed.

The schedule for assessments for this trial is summarised in the following flowchart:

Table 11-1 Schedule of Assessments

Schedule	FLOW CHART OF STUDY				
	Visit 1 Screening (up to 7 days)	Visit 2 Randomisation (Day 0)	Visit 3 End of study (Day 8) (between Day 7 and Day 10)	Visit ET Replaces Visit 3 if early termination (Day 1 to 6)	
Informed consent	X				
Assess inclusion-/exclusion criteria and suitability for study	X	X			
Record demographics, assess concomitant medication and relevant medical history	X	X			
Physical exam, collection of blood samples for haematology & biochemistry, vital signs	X		X	X	
Urine pregnancy test	X		X	X	
12-lead ECG	X				
Endoscopy	X				
Investigator's assessment of GERD status	X				
Make appointment for next visit	X	X			
Randomisation		X			
Dispense study medication & emergency card provided		X			
Patient completes RDQ questionnaire.		X	X	X	
Record AEs and concomitant medication		X	X	X	
Collect returned medication, assess compliance with study medication.			X	X	
Complete OTE			X	X	

* Previous endoscopy results may be used if conducted prior to consent within 28 days of giving consent and if the examination was conducted at the same hospital

** OTE: Overall Treatment Evaluation.

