13.1.2 Observation Period for Adverse Event Reporting

The observation period for an individual patient will start after giving informed consent and will finish at the last visit defining the end of the study for the given individual patient.

Any SAEs occurring after Informed Consent must be reported.

Any untoward medical events occurring after Informed Consent but prior to IMP administration should be recorded in the patient's medical history and not reported as an AE.

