13.1.3 Information to be Collected on Adverse Events

Each AE will be recorded according to the criteria given below. "Relationship to IMP" must be determined by the Investigator (if medically qualified) or by a medically qualified Co-Investigator.

Table 13-1 Table of Information to be Collected on Adverse Events

Variable	Category	Definition
AE reported term		Any untoward medical occurrence in a patient administered an IMP and which does not necessarily have to have a causal relationship with this treatment. An AE can therefore be any unfavourable and unintended sign (including an abnormal laboratory finding, for example), symptom, or disease temporally associated with the use of a medicinal product, whether or not considered related to the IMP.
Date AE started		The date on which the AE started.
Date of change in severity of AE		The date on which the AE changed in severity. This date equates to the finish date of the old severity and the onset date of the new severity.
Intensity	Mild Moderate Severe	Intensity will be determined by the Investigator. For symptomatic AEs the following definitions will be applied, but medical experience and judgement should also be used in the assessment of intensity. The AE does not limit usual activities; the patient may experience slight discomfort. The AE results in some limitation of usual activities; the patient may experience significant discomfort. The AE results in an inability to carry out usual activities; the patient may experience intolerable discomfort or pain.
Actions taken	None IMP dose changed IMP permanently discontinued Symptomatic therapy Patient hospitalised or hospitalisation prolonged Other action (specify)	No action was taken in relation to this AE. The dose of IMP was changed due to this AE, i.e. increase, decrease, or temporary discontinuation. The IMP was permanently discontinued due to this AE. Symptomatic therapy was added or changed due to this AE. The patient was hospitalised or hospitalisation was prolonged due to this AE. Other action was taken due to this AE, e.g. diagnostic tests, laboratories and procedures.
Relationship to IMP	Unassessable/ Unclassifiable	Insufficient information to be able to make an assessment.

Variable	Category	Definition
	Conditional/ Unclassified	Insufficient information to make an assessment at present (causality is conditional on additional information).
	Unrelated	No possibility that the AE was caused by the IMP.

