16.1 ADVERSE EVENTS

Adverse Events (AEs) will be coded using MedDRA version 17.0. For an individual patient, only adverse events commencing after first dose of IMP and no later than last dose of IMP+1day will be included in the AE and serious adverse event (SAE) summaries. AEs that began prior to the first dose of IMP or more than one day after the final dose of IMP will not be included in the analysis. Where an AE start date is partially or completely missing, and it is unclear using partial dates as to whether the AE is treatment-emergent, it will be assumed that it is.

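### AEs enter the analysis by start date alone, with no rule for a pre-dose complaint that worsens on treatment, so counting depends on how each site records it

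*Protocol*

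**What the plan says.** **Analysis window.** Protocol 14.5.1: "AEs that began prior to the first dose of IMP or more than one day after the final dose of IMP will not be included". SAP 16.1 repeats this and adds that "only adverse events commencing after first dose of IMP and no later than last dose of IMP+1day will be included" in the AE and SAE summaries. An unclear or missing start date is resolved in favour of treatment-emergent. Neither section mentions a change in severity.

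**Recording before the first dose.** Protocol 13.1.2 opens with "The observation period for an individual patient will start after giving informed consent". It then says that untoward events between consent and dosing "should be recorded in the patient's medical history and not reported as an AE", while SAEs after consent must still be reported. Protocol 13.1.4 has AEs that arise after dosing entered in the CRF.

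**Visit 2.** Table 11-1 marks Visit 2 in the row "Record AEs and concomitant medication". Protocol 9.6.1 says that patients at Visit 2 will "have any adverse events and concomitant medications recorded", and 3.10 agrees. Protocol 11.3.2.1, describing the same visit, asks for changes in medical history and does not mention AEs.

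**Severity changes.** Table 13-1 in Protocol 13.1.3 has a field defined as "The date on which the AE changed in severity", and treats that date as the onset of the new severity. Protocol 11.7.1 counts significant clinical deterioration as an AE.

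**Day 0.** SAP 7.1 sets Day 0 at randomisation. SAP 7.2 treats AEs that start on that day as post-baseline.

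**The concern.** The stated safety endpoint is the proportion of patients with AEs. It is compared between arms by Fisher's exact test for all, related and severe AEs (Protocol 14.5.1, SAP 16.1.1). A complaint that was mild before dosing and becomes severe during the treatment week is something this comparison should treat in one defined way. The plan defines no way. Two patients with the same clinical course can therefore fall on opposite sides of the analysis because their sites filled in different forms. The planned 25 to 50 sites, with conflicting instructions for Visit 2, make uniform practice unlikely.

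At stake is the completeness of the AE count and the reproducibility of the treatment-emergent classification. The efficacy analysis is not affected.

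**Working it through.** The point turns on text, so the check sets the provisions side by side. The only arithmetic is a count of days.

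**Step 1: are events found at Visit 2 pre-dose?** Protocol 3.10, 11.3.2.1 and 12.4 tell patients to start tablets the day after Visit 2. SAP 14.1 derives the first administration date as the day after dispensing. Any event found at Visit 2 has therefore begun before the first dose. (Protocol 9.5 and SAP 4.1 speak of the treatment period as commencing at Visit 2. Even so, in the Protocol 3.10 account, AEs at Visit 2 are recorded before medication is dispensed.)

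**Step 2: can the Visit 2 instructions all be followed?** For a non-serious event, Protocol 3.10, 9.6.1 and Table 11-1 lead to an AE record. Protocol 11.3.2.1, 13.1.2 and 13.1.4 lead to medical history. For that event they conflict.

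**Step 3: follow one course through each route.** Take a non-serious complaint that starts between consent and first dose and worsens on treatment.

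| How the site records it | Start date seen by the analysis | Result under Protocol 14.5.1 and SAP 16.1 |
|---|---|---|
| Medical history, then a new AE dated at the worsening | On treatment | Counted |
| Medical history, no further entry | None | Not counted |
| AE form at Visit 2, worsening noted as a severity change on that record | Pre-dose | Excluded |
| AE form at Visit 2, then a separate AE dated at the worsening | On treatment for the second entry | Counted |

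The same course is counted in two rows and lost in two. In the second row the condition reaches only the tables in SAP 12, by system organ class and preferred term, without severity or change. In the third row the date needed to detect the worsening has been collected, but no analysis rule uses it. The worst-severity rule in SAP 16.1.1.1 does not help, because it does not override the start-date window in SAP 16.1.

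**Step 4: Day 0 in the SAP.** An AE that starts on Day 0 is post-baseline under SAP 7.2. With the first dose on Day 1 (SAP 14.1), it precedes dosing and is excluded under SAP 16.1. The two labels do not agree.

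**Step 5: how long is the affected period?**
- Consent to first dose: up to 7 days of screening + 1 day = about 8 days.
- AE analysis window: 7 dosing days + 1 day = about 8 days.

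The period in which a complaint can begin before dosing may be as long as the period analysed.

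**Step 6: size.** The documents give no AE rate, no rate of pre-dose complaints and no frequency of worsening. The number of events lost cannot be derived, and any power figure would only reflect the rates chosen for it.

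**The case against.** The strongest reply is that the plan does not bar worsening events. Protocol 11.7.1 calls significant deterioration an AE. Table 13-1 gives a new severity its own onset date and asks whether the patient has had the event before, so the form expects AEs in people with a prior history. Protocol 13.1.4 requires AEs arising after dosing to be recorded. This stands. A reader might infer that a complaint which worsens on study drug is never counted, and the documents do not support that. A site that follows 13.1.2 and then enters the worsening as a new AE will have it counted. What remains is that no text tells the site to do so for a complaint already in medical history.

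Second, the Visit 2 conflict is partly reconcilable. SAEs are reportable from consent, so asking about events at Visit 2 has a purpose, and a non-serious event that starts before dosing and does not change stays out of the AE analysis by either route. That is right for stable events. For worsening events the route matters, as the table in the working shows.

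Third, sending pre-dose events to medical history is a legitimate design choice. Agreed; it need not be overturned.

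Fourth, there are other views of harm: laboratory and vital-sign changes, physical-examination shift tables, and withdrawals by reason. These are partial safeguards, but none feeds the proportion of patients with AEs.

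Fifth, both arms are blinded and subject to the same rules. This limits the claim about bias.

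**Conclusion.** The point holds as a gap in definition together with a conflict in recording instructions. Inclusion rests on start date alone, no rule covers worsening of a pre-dose complaint, and the Visit 2 text invites different practice between sites. SAP 7.2 and SAP 16.1 also disagree on events that start on Day 0.

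The consequence is a possible under-count of AEs in both arms. It is tempting to say that the comparison is biased towards no difference. That follows only if the drug causes more worsening than placebo, and the documents do not show this. Otherwise the loss falls on both arms alike. The size is unknown, because the plan gives no rates. The day count (about 8 days against about 8 days) shows that the pre-dose period is not negligible, but it does not show how many events are lost.

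The conclusion assumes that first dose falls on Day 1, as in Protocol 12.4 and SAP 14.1, and that the AE window is programmed literally from the recorded start date. It is a cheap improvement to the safety analysis and does not threaten the primary result.

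**What to change.** 1. In Protocol 14.5.1 and SAP 16.1, define the analysed events as any event that starts, or any pre-dose condition (including one held in medical history) that increases in severity, from first dose to last dose plus one day.
2. Take the date of worsening as onset. For an event already on the AE form, use the severity-change date in Table 13-1. For a condition in medical history, require a new AE entry dated at the worsening.
3. Make Protocol 3.10, 9.6.1 and Table 11-1 agree with 11.3.2.1, 13.1.2 and 13.1.4 on what is recorded at Visit 2. Moving all pre-dose events onto AE forms is not required; either route works once item 2 is in place.
4. Align the Day 0 statement in SAP 7.2 with the window in SAP 16.1.

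The cost is minor wording in both documents and a small programming change. Reported AE rates may be slightly higher.

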14.5.2 Laboratory Data

For the purpose of analysing laboratory data, "baseline" is defined as the baseline assessments at Visit 1, screening and "last visit" is defined as the final visit, Visit 3 or the Early Termination Visit.

Each pre-study baseline laboratory value will be categorised as low, normal, or high based on the reference range. Each post-baseline value will be classified in a similar manner, producing a 3 x 3 table for each treatment group at each post-baseline visit. Scores of "1" will be assigned to low values, "2" to normal values, and "3" to high values. Using these scores, shifts from baseline will also be assigned a score. For example, a laboratory value that shifts from low to high will be assigned a score of 2, whilst a laboratory value that remains at a low value will be assigned a score of 0. Shifts between these categories between baseline and subsequent timepoints will be compared using the Wilcoxon Signed-Rank test within each treatment group. Statistical testing will be performed at last visit.

At each visit, summary statistics for the absolute laboratory value and the changes from baseline will be presented by treatment group. The significance of within-treatment changes from baseline will be assessed using the Wilcoxon Signed-Rank Test. The significance of between treatment changes from baseline will be assessed using the Wilcoxon Rank-Sum Test. Statistical testing will be performed at last visit.

Scatter plots of end of treatment values versus baseline values will be provided for all laboratory tests.

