2. Calcium carbonate – high doses of calcium may cause alkalosis, hypercalcaemia, acid rebound, milk alkali syndrome or constipation.

For this reason, the risk benefit balance for the current study is considered to be acceptable

This study will be conducted in accordance with the principles set out in the Declaration of Helsinki. It will comply with International Conference on Harmonisation (ICH) Good Clinical Practice (GCP) and applicable regulatory requirements.

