10 STUDY POPULATION

10.1 Inclusion Criteria

Only patients to whom all of the following conditions apply will be included:

1. Informed consent has been obtained.
2. Age: ≥ 18 to ≤ 65 years
3. Sex: male or female.
4. Primary diagnosis: Current evidence of symptomatic GERD in accord with the Montreal definition [1,14]. This evidence can be based solely on symptom characteristics. Patients should have a GERD history of frequent episodes of GERD-related symptoms during the last 3 months and also during 5 of the last 7 days prior to study screening.
5. GERD Status: Patients will be patients at the clinic or members of the public who respond to an advertisement or via their doctor. Patients must have had troublesome heartburn and/or regurgitation (with or without dyspepsia symptoms) of at least mild or moderate intensity* on at least five days during the week before the start of screening. If the patient also has other symptoms, the heartburn, regurgitation or dyspepsia should be the predominant symptoms.

*Symptom intensity should be assessed using the following scale;

- Mild: awareness of symptom but easily tolerated
- Moderate: discomforting symptom sufficient to cause interference with normal activities including sleep
- Severe: incapacitating symptom with inability to perform normal activities, including sleep

6. Patients who have not taken any antacids within 24 hours before randomisation (Visit 2) and be instructed not to take antacids throughout the remainder of the study.
7. Patients taking mucous membrane protection drugs or prokinetics may enter the study provided that these are discontinued for at least 5 days before screening and throughout the remainder of the study.

8. Systemic glucocorticosteroids or non-steroidal anti-inflammatory drugs (NSAIDs, except for low dose aspirin which can be given for cardioprotection) can only be taken for up to 3 consecutive days in the 28 days prior to screening
9. Absence of relevant abnormalities in the physical examination, endoscopy, ECG and laboratory safety results.
10. Patients must be sufficiently literate to be able to complete the RDQ unaided.

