or Early Termination Visit) will be compared using the Wilcoxon Signed-Rank test within each treatment group. Statistical testing will be performed at last visit.

In addition to the high and low quantitative laboratory assignments (as identified by means of the laboratory reference ranges), clinically significant quantitative laboratory assessments will be identified by investigator and the result will be recorded in the eCRF. The number and percentage of patients with abnormal or clinically significant results will be tabulated by treatment groups by visit. The results will also be listed.

Women of child-bearing potential will undergo urine pregnancy testing (positive or negative). The results will be listed.

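### Laboratory category shifts are tested only within each arm, on a signed score in which opposite shifts cancel, so the test can flag drift common to both arms or miss an excess of new abnormal values over placebo

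*Protocol*

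**What the plan says.** Protocol 14.5.2 classifies each baseline and post-baseline laboratory value as low, normal or high against the reference range and scores the categories 1, 2 and 3. The worked example fixes the sign: "a laboratory value that shifts from low to high will be assigned a score of 2", and a value that stays low scores 0. The shift is therefore last-visit score minus baseline score.

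The only test of these shifts is: "Shifts between these categories between baseline and subsequent timepoints will be compared using the Wilcoxon Signed-Rank test within each treatment group". SAP 16.3 repeats the scoring and the test: shifts "will be compared using the Wilcoxon Signed-Rank test within each treatment group", at the last visit.

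The same sections contain two other relevant items:
- For the measured values, not the categories, Protocol 14.5.2 and SAP 16.3 plan a between-arm test: "The significance of between treatment changes from baseline will be assessed using the Wilcoxon Rank-Sum Test".
- SAP 16.3 adds a table without a test: "The number and percentage of patients with abnormal or clinically significant results will be tabulated by treatment groups by visit".

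Neither document plans a between-arm test of category shifts or of new abnormal values for each analyte.

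The entry criteria in Protocol 10.1 require: "Absence of relevant abnormalities in the physical examination, endoscopy, ECG and laboratory safety results".

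**The concern.** There are two separate weaknesses.

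**No control.** A signed-rank test within one arm asks whether that arm moved from baseline. It does not ask whether drug differs from placebo. Patients enter without relevant laboratory abnormalities, so some movement out of the normal range can occur in both arms with no drug effect, and the test can be significant in each arm for that reason alone.

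**A signed net score.** The score records direction along the scale, not whether the patient got worse. Normal-to-high is +1 and normal-to-low is −1, so two worsenings cancel. High-to-normal is −1 and cancels with normal-to-high. Low-to-normal, an improvement, is +1 and adds to normal-to-high. An excess of new abnormal values over placebo can therefore leave the test statistic near zero.

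What is at stake is how the laboratory safety tables are read. Protocol section 6 lists raised plasma sodium among the adverse reactions and, for calcium carbonate, says "high doses of calcium may cause alkalosis, hypercalcaemia". Sodium and calcium are both measured. For such risks the event of interest is a patient crossing the upper limit, and the test aimed at crossings leaves out the placebo arm.

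**Working it through.** **Inputs from the documents**
- Scores: low 1, normal 2, high 3 (Protocol 14.5.2).
- Patients per arm: 527 (Protocol 9.4).
- Level: 5%, two-sided (SAP 7.4).
- Analytes: 5 haematology + 10 chemistry = 15 (SAP Appendix 1).

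The documents give no shift rates. Every count and rate of shifts below is an assumption.

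**1. The plan's own figures.** An exact two-sample t-test calculation for effect size 0.2, 90% power and two-sided 5% gives 526.33 per arm, rounded up to 527, or 1054 in total, as stated. Last-visit score minus baseline score gives low-to-high = 3 − 1 = 2 and low-to-low = 1 − 1 = 0, matching the worked example.

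**2. All possible shift scores**

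| Baseline | to low | to normal | to high |
|---|---|---|---|
| low | 0 | +1 | +2 |
| normal | −1 | 0 | +1 |
| high | −2 | −1 | 0 |

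**3. Form of the test.** With zeros dropped and all remaining shifts of size 1, the signed-rank test reduces to a sign test. With u shifts up and d down, z = |u − d| / √(u + d) by the normal approximation.

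**4. Two worsenings that cancel** (needs no abnormal baseline values)
- Active: 20 normal-to-high, 20 normal-to-low. z = 0/√40 = 0, p = 1.0.
- Placebo: 7 and 7. z = 0/√14 = 0, p = 1.0.
- New abnormal values: 40/527 (7.6%) v 14/527 (2.7%), Fisher p = 0.0004.
- New high values: 20/527 (3.8%) v 7/527 (1.3%), Fisher p = 0.018. New low values are the same by construction.

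**5. Drift common to both arms**
- Each arm: 30 normal-to-high, 10 high-to-normal. z = 20/√40 = 3.16, p = 0.0016 in each arm.
- New abnormal values: 30 v 30, Fisher p = 1.

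**6. Chance of p < 0.05**, 4000 simulated trials per row, 527 per arm (N normal, H high, L low)

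| Assumed rates | Planned test, active | Planned test, placebo | Fisher on new abnormal values |
|---|---|---|---|
| Active N→H 4%, N→L 4%; placebo 1.5% each | 5.3% | 5.1% | 94.0% |
| Both arms N→H 6%, H→N 2% | 91.1% | 92.4% | 4.1% |
| Both arms N→H 4%, H→N 2% | 46.2% | 47.9% | 3.2% |
| Active N→H 6%, H→N 2%; placebo 2% each | 91.7% | 5.3% | 90.8% |

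The last row shows that the planned test does detect a clear one-way rise. A between-arm rank-sum test on the same signed score would not cure the cancelling: in the first row it is significant in 5.0% of trials.

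**7. Number of shift tests.** 15 analytes × 2 arms = 30. Expected below 0.05 by chance: 30 × 0.05 = 1.5. If the tests were independent (an assumption), the chance of at least one is 1 − 0.95^30 = 78.5%.

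**The case against.** The strongest reply is that this is one test within a laboratory analysis that does use the placebo arm elsewhere:
- Continuous changes are compared between arms by rank-sum. A general upward movement in calcium or sodium is what that test targets.
- The 3 x 3 tables and the SAP's table of abnormal or clinically significant results are shown by arm.
- Protocol 14.5.2 also plans scatter plots of end-of-treatment against baseline values.
- Under Protocol 13.1.4 a significant laboratory abnormality can be recorded as an adverse event, and adverse events are compared between arms by Fisher's exact test (Protocol 14.5.1, SAP 16.1.1).

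All of this stands, and it limits the weight of the point. A reader might infer that laboratory safety is analysed without a control comparison. The documents do not support that. What remains is narrower: the rank-sum test can miss a few patients crossing a limit, the tables carry no test, and the adverse-event comparison is aggregate rather than per analyte.

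A second reply is that cancelling is a contrived case. For high-to-normal shifts this is partly right. The entry criterion limits how many patients are high at baseline, and exact balance is a chosen worst case. With 16 up and 4 down, an exact sign test gives p = 0.012, so the rise is flagged. If normalising shifts were as common on placebo, with say 3 up and 16 down there, placebo would show p = 0.004 beside p = 1.0 for 16 up and 16 down on active, and a reader would notice the contrast. When the two cancel exactly, the number high on active has not risen from baseline; the missed excess is relative to placebo. Cancelling of normal-to-high with normal-to-low needs no abnormal baseline values, so the entry criterion does not prevent it.

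A third reply is that the named risks are remote here. Protocol section 6 ties hypercalcaemia to high calcium doses and says the minimum dose is studied. Known hypercalcaemia and low-sodium diets are excluded, and treatment lasts 7 days. This also stands as a limit on the consequence.

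**Conclusion.** The point holds for the category-shift test. As written, the test does not compare drug with placebo, and its signed score lets opposite shifts cancel. It can therefore be significant in both arms with no drug effect (91.1% and 92.4% of simulated trials under one assumed drift), or stay at p = 1.0 in both arms while new abnormal values are 40 v 14. These sizes rest on assumed shift counts and rates; the structure of the test does not.

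Two stronger readings go too far. One is that the test will miss a drug-related rise: it can, but a clear one-way rise on active is detected in 91.7% of simulated trials. The other is a count of 60 tests, reached by adding the within-arm tests of continuous changes. The shift tests number 30, with about 1.5 expected below 0.05 by chance.

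This is a supplementary safety analysis. No endpoint, stopping rule or confirmatory claim depends on it, and the primary result is unaffected. It is a worthwhile improvement, not a necessary correction.

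**What to change.** In SAP 16.3:
1. Keep the 3 x 3 shift tables by arm, and show within-arm shifts without p-values.
2. Replace the within-arm signed-rank test of shifts with a between-arm Fisher's exact comparison, per analyte, of patients newly high at last visit (high then, not high at baseline) and, separately, newly low. Report the difference in proportions with a 95% CI.
3. Label these comparisons descriptive and unadjusted for multiplicity.

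Testing high and low separately removes the cancelling, and the plan already uses Fisher's test for adverse events.

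The replacement has limits that should be stated. It is still 15 × 2 = 30 tests, and power is low for rare shifts: at 527 per arm, 10 v 3 gives p = 0.09 and 16 v 8 gives p = 0.15. The intervals will be more informative than the p-values.

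Cost: SAP wording and one replacement table. No new data are needed.
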